Recruitment and Consent Procedures: Patient recruitment was initiated on November 7th, 2017 with expected enrollment completion in April 2019. The trial is currently recruiting patients at UCONN Dialysis/DCI and DCI Manchester. The recruitment strategy includes study fliers posted in different locations including UCONN Health Nephrology, Dental Clinics and Dialysis Outpatient Units. All recruitment strategies and material were approved by UCONN Institutional Review Board (IRB) and DCI ARO. Figure 2 represents study flow chart.

The initial patient selection is based upon administrative and medical record review by the nurse manager with the utilization of the study's pre-screening form. The nephrologist reviews the patient selection and, based on clinical judgment and the pre-screening criteria makes the recommendation. We have also developed recruitment tools (pre-screening forms, study brochures), which are practical and easy to implement in order to assist the nephrologist and dialysis personnel during the pre-screening process. Once the pre-screening process is completed and the patient agrees to be approached, the study coordinator meets with the ESRD patient to present the study, the overall risk/benefits analysis, written consent is sought from each of the participants. The consent process may be extended to more than one meeting given the patient's level of fatigue [37].

Randomization and Allocation: The study follows a block randomization scheme. Blocks will be determined as per 2X2X2 a priori categorization of age, race and gender. More specifically, the participants in two dialysis units (UCONN Dialysis/DCI and DCI Manchester) will be randomly assigned to the study arms using a computer randomization program supervised by the study's biostatistician. Once sequences are determined, they remained concealed in opaque envelopes and opened prior to enrollment in the unit by the study coordinator.

Examiner calibration: The calibrated dental hygienist practices under the supervision of the Principle Investigator (PI). Following the calibration process, there was an agreement within ± 1 mm of 96%. Blinding: At 6-month visit, the final assessment will be conducted by the PI, who will be blinded to the study arm.

Methods of Data Collection and Types of Data to be collected (may refer to attached surveys/ forms etc.) *Medical data collection:* Once enrollment is completed, demographic, anthropometric, medical history data will be collected using a standardized data extraction form at baseline. The biochemical data will include serum albumin, dialysis adequacy (Kt/V), vitamin D levels. Potential confounders will include race, history and duration of diabetes, diabetic control, smoking history, history of CVD, body mass index (BMI), history of peripheral arterial disease and comorbid conditions. Additionally, in order to assess the magnitude of comorbidities, we will use the Charlson Comorbidity Score, which has been validated in ESRD and found appropriate to assess comorbidity prognostic impact⁷⁴. Biochemical data will be examined at every study time point to assess medical changes.

Periodontal Data: Full mouth periodontal examination will include: numbers of missing teeth, pocket depth (PD), clinical attachment level (CAL), plaque score (PS), bleeding on probing (BOP). PS (O'Leary) is a dichotomous measure with the use of disclosing solution at six sites of all teeth. Pocket depth (PD) is the distance from the gingival margin to the base of the pocket is measured in mm. Bleeding on Probing (BOP) is scored after probing depth measurements are taken. Clinical attachment level (CAL) represents the distance from the cemento-enamel junction to the base of the pocket in mm. For all measures, six sites around each tooth will be examined: mesial-buccal, distal-buccal, distal-lingual, lingual and mesial-lingual.

Blood Collection and Analyses: Blood samples will be drawn prior to dialysis session at each participating dialysis unit. Samples will be centrifuged at 3000rpm for 15 minutes and then transported on ice. Samples will be coded and stored at -70°C. IL-6 and hsCRP levels will analyzed in dublicate by ELISA with kits from BioSource International (Carmillo, CA) and Diagnostic Systems Laboratories (Webster, TX). Oxidative stress markers will be quantified by simultaneous measurements of F2-isoprostane and isofuran concentrations with gas chromatography as described before ²³. Serum albumin will be measured by enhanced chemiluminescence immunoassay on Roche Modular Analyzer (Roche Diagnostics, Indianapolis, IN).

Statistical methods: All analyses will follow the intent-to-treat principle. Given an attrition of rate of approximately 30% in the dialysis population, missing data will likely be from different sources (e. g., failure to complete questionnaire, study dropout, death). We will, therefore, utilize the multiple imputation algorithms of the IBM SPSS Missing Values 22 software[39, 40] to impute missing data. Data will be screened as recommended[41]. Standard diagnostic procedures will examine whether multivariate outliers exist, as well test for deviations from normality and linearity among dependent measures. When continuous measures are skewed, linear transformation will be attempted in order to preserve the inherent power of the continuous metric[42]. Descriptive analysis for all four time points will be including continuous measures with means, medians and standard deviations. Given OHIP-14 responses are ordinal, we will calculate the responses based on the "simple count", score frequencies as used before[43] and analyzed with non-parametric methods. Spearman correlation analysis will be used to test associations between clinical parameters and patient's oral health perception. In order to assess the effect of the confounding factors on oral response, univariate model will correlate PD and CAL changes with the baseline parameters, demographic, socioeconomic status variables, as well as diabetic control, dialysis adequacy and vintage, vitamin D levels.

Exploratory univariate analysis and test statistics will be conducted to examine variable distribution. Outliers defined as more than two standard deviations from the mean will be detected. All biomarker variables will be tested for normality and logarithmically transformed if not normal. All analyses will include means and standard deviations for continuous variables and percentages for categorical variables. For skewed variables, analyses will show median and interquartile ranges. CRP and IL-6 changes (Δ CRP and Δ IL6) will be the dependent variables for hypothesis testing between the two arms. We will use a 3-level (time, subject, and cluster) hierarchical linear modeling technique[44] in the analysis of the data. The intercept (as a more robust indicator of initial baseline status) and slope (as an indicator for change, modeled as linear) are created for each subject. Predictors of inflammatory response will be assessed at subject level as well as subject nested within arm/recruitment site level. Additional secondary analyses will assess changes in the nutritional markers. The HLM will isolate predictors of inflammatory and oxidative stress response based on clinical phenotype, medical confounders, and cluster data.

Retention efforts: Physical limitations and fatigue, which may prevent this population from independent everyday transportation, have been identified as major reasons for research study participation in this population [38]. Hence, to overcome these difficulties, we have developed a community-based model, which has been effective with the retention and adherence rates. Based on this model, we will utilize a mobile dental unit that facilitates examinations and periodontal therapy in the isolation room of each hemodialysis unit. The isolation room secures privacy for both patient and provider. We systematically review our recruitment and retention rates as well as feedback from patients in the team's monthly meetings.

DATA AND SAFETY MONITORING PLAN

We have a Data and Safety Monitoring Plan in place, which will be submitted and approved by the IRB. Based on this plan, the data will be reviewed annually. Given that the clinical protocol procedures in the proposed study are standard of care procedures with minimal/slight increase over minimal risk, the individuals performing the safety monitoring will be the PI, the study coordinator, an institutional colleague, who is not involved in the study, and the IRB.

The data used for safety monitoring will be data related to:

- 1. Serious adverse events.
- 2. Dropout rates and reasons for the dropouts,
- 3. Enrollment numbers,
- 4. Analysis of outcome data and its relationship to potential changes in study design.
- 5. Protocol deviations
- 6. Un-blinded data

IRB Review
IRB NUMBER: 16-111-1
IRB APPROVAL DATE: 06/07/2018

Version 10; May 07, 2018

During the course of the study, a copy/summary of the monitor reports and/or minutes will be submitted to the IRB, Clinical Research Center (CRC) and NIH. The PI will evaluate the adverse events and determine whether the adverse events affect the risk/benefit ratio of the study and if modifications in the protocol and/or consent form are needed. In case of adverse events, the PI will report them to IRB, CRC, and NIH.

Protection of Confidentiality: The study will be conducted under the supervision of the PI, the co-Investigators and the collaborators. Best medical practices will followed during all procedures. All dialysis units are staffed with qualified and licensed personnel prepared to address emergencies. Further, nephrologist/attending is present at the dialysis units to clear the patient's medical status. During the course of the study, a copy/summary of the monitor reports and/or minutes will be submitted to the IRB, Clinical Research Center (CRC) and NIH. The PI will evaluate the adverse events and determine whether the adverse events affect the risk/benefit ratio of the study and if modifications in the protocol and/or consent form are needed. In case of adverse events, the PI will report them to IRB, CRC, and NIH, Study data will be maintained in a separate research record. All materials and data will be coded with number combinations. The code linking the study data to identifiers will be in the PI's computer protected by password. All study records will be coded in a locked cabinet in a secure area accessible only to research staff. A copy of the consent will be placed in the dialysis unit medical record. All electronic records (e.g. database, spreadsheets) will be password protected. Any computer hosting such files will have password protection to prevent access by unauthorized users. Access to study data will be restricted to the PI and Co-Is as well as the study key personnel. Data that will be shared with others will be coded to confidentiality protection.

Study Management: At the study initiation meeting, a delegation of responsibilities was carried out according to which, each investigator, and study personnel agreed to their assigned roles. The study PI has been in charge of the execution of this plan. Roles were assigned as justified in the research grant proposal. At the end of the initiation meeting, a study flow sheet was developed with all study procedures and practices. The flow sheet follows the study clinical schema as presented above. The flow sheet guarantees that all study activities are completed in the specific time points as described in the research strategy and the endpoints and outcomes are reached.

The study coordinator has been in charge of the regulatory management of the study, which includes the development of the regulatory binder with all essential documents. The regulatory binder includes study protocol, the study personnel human subject training log, the delegation of responsibilities form, the prescreening and screening forms, consent forms, HIPAA forms, serious adverse events list, protocol deviation reports, and IRB approvals. The study subject chart contains all information about each study visit dated appropriately and precisely as well as a note declaring the procedures completed per visit. The pre-screening form is part of the chart. De-identified subjects that fail pre-screening are also maintained in a separate file. The study coordinator maintains a master subject log list, where all visits of all subjects are securely listed. This list guarantees accurate scheduling based on study time points.

The PI and the study coordinator are in charge for reporting the adverse events and also the follow up visit with the subject. Further, any protocol deviation is documented and reported. All laboratory assessments are maintained in a log list with specimen numbers and dates. An important part of the study is the quality management plan, which ensures study quality and adherence to the protocol standards. To achieve this, we have established an extensive monitoring plan to secure the study design, and achieve the endpoints and outcomes. Weekly study team communication and meetings are scheduled to prevent any misunderstandings or protocol gaps. The meetings help the team resolve problems and move to corrective actions at once before they become an established pattern. Every three months, the study subject charts are audited internally. To ensure the presence of consent form, pre-screen and screening form, lab requests, data collection forms, missed appointments and notes. Further, the electronic data files and all data variables are crosschecked with the source original data. The subject ID will be also crosschecked. Missing data will be left blank. Merging files of laboratory and clinical variables will be performed carefully based on ID variable.

Study Rigor and Transparency: The proposed trial follows a rigorous and transparent study design as requiring by the NIH capturing elements of trail design, pre-specified eligibility criteria, pre-specified primary and secondary outcomes, detailed intervention description to allow replication, intervention random allocation and concealment, blinding in outcome assessment, appropriate sample size calculations, explanation of interim analysis, as per CONSORT Guidelines[45, 46]. The proposed methods secures a robust and unbiased analysis as expected in a randomized controlled trial (RCT) and will ensure reproducibility of the experimental design[47]. With these efforts, we acknowledge the importance of research transparency through updated trial status, result and data reporting on Clinicaltrials.gov, as expected[48].

Timetable: Test Arm

Intervention	Visit 1	Visit 2 Baseline	Visit 3-4 Day 0	Visit 5 1-month	Visit 6 2-month	Visit 7 3-month	Visit 8 4-month	Visit 9 5-month	Visit 10 6-month
Consent Form	x								
Medical History	x								
Review/Vitals									
Periodontal	x								
Screening									
Full mouth		x			x		x		x
periodontal exam									
OHIP-14		x			x		x		x
Periodontal			x						
Therapy (Deep									
periodontal									
cleaning)									
Oral hygiene/			x	x	x	x	x	x	x
Behavioral									
modification									
Maintenance					x		x		x
(Tooth Cleaning)									
Inflammatory		x			x		x		x
Markers									
(CRP, IL-6)									
Oxidative stress		x			x		x		x
(F2 isoprostanes,									
isofurans)									
Nutritional		x			x		x		x
Markers									
(Albumin)									

Control Arm (The shaded columns symbolize absence of study activities)

Intervention	Visit 1	Visit 2 Baseline	Visit 3-4 Dau 0	1-month	Visit 5 2-month	3-month	Visit 6	5-month	Visit 7 6-month
Consent Form	x	Duottite	Dugo	1 month	_ mones	Jinonen	4 months	Jinonen	o monen
Medical History	x								

IRB APPROVAL DATE: 06/07/2018

Review/Vitals						
Periodontal	x					
Screening						
Full mouth		x		x	x	x
periodontal exam						
OHIP-14		x		x	x	x
Periodontal			x			
Therapy (Deep						
periodontal						
cleaning)						
Oral hygiene/			x			x
Behavioral						
modification						
Maintenance						x
(Tooth Cleaning)						
Inflammatory		x		x	x	x
Markers						
(CRP, IL-6)						
Oxidative stress		x		x	x	x
(F2 isoprostanes,						
isofurans)						
Nutritional		x		x	x	x
Markers						
(Albumin)						

${\bf Standard\ Protocol\ time points\ and\ items\ based\ on\ SPIRIT\ guidelines.}$

	STUDY PERIOD Enrollment Post-allocation								
		Enrollment Baseline		Close-out					
TIMEPOINT**	-t ₂		to	t_1	t ₂	t ₃	t ₄	t ₅	t ₆
Nephrology Pre- screening	X								
Informed Consent		X							
Periodontal Screening		X							
Allocation		X							
INTERVENTIONS:									
Arm 1: Repeated Interventions +									
Behavioral Modification									
Arm 2: Control/Standard of Care			X						X
ASSESSMENTS:									
Demographic Data		X							
Biochemical Data		X							

Inflammatory Markers	X		X	X	X
Oxidative Stress Markers	X		X	X	X
Nutritional Markers	X		X	X	X
OHIP-14	X		X	X	X
Periodontal Parameters	X		X	X	X
Adverse Events		X			

[Provide a detailed timetable scheduling all aspects of the research. This will include data collection (e.g. time taken to administer questionnaires, complete interviews, abstract data from charts), analyze data, write reports etc. You may reference an attached flow diagram, including expected start and completion dates, and/or describe the time table here]:

Expected Start Date: May 2016

General Time Table:

6-months: Complete the regulatory requirements, present the protocol in our recruitment sites and start recruitment.

12-months: Complete recruitment and treatment of 20 patients-Collect and transfer blood samples to the lab.

18-months: Complete recruitment and treatment of 20 patients-collect and transfer blood samples to the lab.

24-months: Complete follow-ups, perform biomarker lab analyses, compile and analyze data.

- Expected Completion Date: November 2018
- **6. Budget / resources:** [You need to think about what you will need for your research and whether those resources are available to you. The IRB will want to know that you have thought carefully about what resources are needed and from where you expect to obtain these, and whether or not a budget workbook needs to be completed. Some types of research are more resource intensive/expensive than others and you will have to consider this when deciding upon your research method.]: The NIH budget is attached.
- 7. Dissemination [Describe how you intend to disseminate the results of your research, e.g. dissertation, presentation, web site, journal article.]: The results of this research project will be presented in national and international meetings as well as in a form of peer-review journal article as expected by NIH.
- 8. References / Literature Review:

- 3. [name], Hall Y, Swede H, [name] J. Periodontitis associated with chronic kidney disease among Mexican Americans. Journal of public health dentistry 2012.
- 5. [name], Swede H. Disparities in Periodontitis Prevalence among Chronic Kidney Disease Patients. Journal of Dental Research 2011;90(6):730-34.

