- Since several drug metabolism and elimination takes place in the kidney, and for protocol adhesion, only analgesics such as acetaminophen and anti-inflammatory drugs such as aspirin will be prescribed and "realistically dosed", resulting to either a dose reduction or prolongation of the dosing interval. If any other anti-inflammatory medication is needed, the patient will be excluded from the study (as per exclusion criteria)
- There is no evidence-based recommendation on the use of prophylactic antibiotics in the dental management of ESRD patients due to the lack of data on the duration and effects of transient bacteremia post dental intervention. Our preliminary study, which was conducted without antibiotics, had in no adverse events to report. Transient bacteremia has been shown to resolve in less than 20min in systemically healthy individuals (Lockhart et al., 2008). Antibiotic overutilization and misuse result in selection of resistant microorganisms and reduced antibiotic efficacy. Therefore, in our study we plan to use antibiotics wisely only if recommended by the primary nephrologist for high-risk patients.

Methods

Study design and Subject selection: The proposed study will be a two parallel arm feasibility clinical trial that will recruit 72 ESRD subjects with periodontitis in a model of computerized block randomization, which will facilitate recruitment in each outpatient dialysis unit. Blocks will be determined as per 2x2x2 a priori categorization of age, race and gender. More specifically, the participants in 2 dialysis units (UCONN Dialysis/ DCI and DCI Manchester) will be randomly assigned to the study arms using a computer randomization program. As a result, once sequences are determined by the statistician, they will be concealed in opaque envelops and opened prior to the first recruitment in the unit. This study will include participants treated with dialysis 3 times a week. Out of 900 ESRD patients in recruitment sites, we estimated approximately 450 patients with periodontitis. Individuals will be included in the

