- *4) Nutrition Biomarkers:* Serum albumin levels have been widely associated with malnutrition and mortality in ESRD ⁸⁴. We will use albumin levels less than 3.6g/dL as cutoff for malnutrition ^{85, 86}. As serum albumin has been associated with poor oral health status ([name] et a. 2013), we will assess changes in these biomarkers as a result oral intervention.
- 5) Adverse Event Frequency (Secondary outcome): For this outcome, pain, swelling, number of analgesics used (continuous) and presence of oral ulcers (dichotomous) will be recorded. More specifically, pain and swelling will be measured by ordinal scale (10cm horizontal Visual Analogue Scale, VAS).

Study Procedures and who will perform them:

Pre-screen Phase:

The nephrologist will review the potential subject's medical record to determine patient eligibility based on the criteria of the Nephrologist Pre-screen Form questions. The nephrologist will present the study to the potential subject and provide DCRC study contact information. If the potential subject is interested in participating, they will call the DCRC. At the time of the phone call from the pre-screened potential subject, the DCRC study staff will read the telephone script and collect name and scheduled dialysis treatment dates and times in order to schedule visit 1.

Visit 1: ESRD subjects will be consented in the dialysis outpatient units. Following the consent, the medical history will be reviewed and vital signs will be tested. During the screening process, brief periodontal examination will be performed to clear the periodontal inclusion criteria.

Visit 2 (Baseline): Full mouth periodontal examination will include: numbers of missing teeth, pocket depth (PD), clinical attachment level (CAL), plaque score (PS), bleeding on probing (BOP). In the same visit the OHIP-14 will be contacted in an interactive form to the both arms. Blood sample (6.5ml) will be collected for baseline inflammatory, oxidative stress and nutritional markers for both arms.

Visits 3-4 (Day 0): Full mouth scaling/root planning (Deep cleaning below the gum line) under local anesthesia will be performed to remove etiologic factors of the disease in both arms in one or 2 appointments. At the end of the visit, both groups will receive oral hygiene instructions.

*After Visits 3-4 test and control arm visits numbers change.

Test arm: (see time table Test arm, pg.14)

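### One protocol sentence opens the allocation sequences before a unit's first recruitment, which would defeat concealment; a second gives a different and ambiguous time

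*Protocol*

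**What the plan says.** The protocol fixes the opening of the envelopes in two places.

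- Methods, Study design and Subject selection. Once the statistician has determined the sequences, "they will be concealed in opaque envelops and opened prior to the first recruitment in the unit". No opener is named.
- Randomization and Allocation. "Once sequences are determined, they remained concealed in opaque envelopes and opened prior to enrollment in the unit by the study coordinator".

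The same part of the protocol describes who does what before a patient enters. Under Recruitment and Consent Procedures, "The initial patient selection is based upon administrative and medical record review by the nurse manager", the nephrologist then makes a recommendation, and "the study coordinator meets with the ESRD patient to present the study", at which point written consent is sought. The Pre-screen Phase gives the first presentation to someone else: "The nephrologist will present the study to the potential subject and provide DCRC study contact information". The Recruitment Strategy puts the oral examination that establishes eligibility after consent.

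On the structure of the sequences the protocol says: "Blocks will be determined as per 2X2X2 a priori categorization of age, race and gender". Study Rigor and Transparency lists allocation concealment among the features of the design.

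**The concern.** Concealment means that nobody involved in approaching, consenting or screening a patient can know the arm until that patient is irrevocably in the trial. The first sentence ties opening to an event of the dialysis unit, its first recruitment, and not to a consented and eligible participant. If it is followed, the list is open for the whole of recruitment in that unit.

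At stake is the comparability of the arms. Someone who knows the next arm can, without intending to, change how or when the study is presented, or how consent and screening are arranged. The patients who agree could then differ between arms. Blocking balances only age, race and gender. The hierarchical model with its medical confounders adjusts for what is measured, not for unmeasured differences in who agrees to take part.

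**Working it through.** No arithmetic applies: no figure in the protocol measures concealment. The check sets the sentences side by side.

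**1. The sentence under Study design and Subject selection.** What is opened is the sequences. The time is before the first recruitment in the unit. Consent, and the eligibility examination that follows it, come later for every patient in that unit. As written, opening therefore precedes both for everyone there.

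**2. Whether an open list reveals a patient's arm.** The blocks are defined by age, race and gender, which can be known before consent because candidates are identified from records. If entries within a block are used in order (an assumption; the protocol does not say), the next entry gives the arm of the next patient in that block.

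**3. The sentence under Randomization and Allocation.** It is uncertain in two respects.

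- *Time.* If enrolment means the start of enrolment in the unit, the result is the same as in step 1. If it means each participant's entry after consent and screening, and envelopes are opened singly, concealment is kept. Neither condition is stated.
- *Opener.* The words naming the study coordinator may belong to the opening or to the enrolment. Only in the first case does the person who presents the study also hold the allocation.

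**4. Whether another part settles it.** No part of the protocol says that envelopes are opened one at a time, or only after consent and confirmed eligibility. The SPIRIT table appears to mark consent, periodontal screening and allocation in one column, so it shows no order among them.

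**5. Order relative to baseline data.** Medical data collection places the demographic and medical baseline data after enrolment is complete. Opening before enrolment therefore precedes those data even on the harmless reading. This is a reason to prefer opening after the Visit 2 measurements.

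**6. Whether later opening would disturb the schedule.** Study Procedures gives both arms the same care through Visits 3-4 and then notes: "After Visits 3-4 test and control arm visits numbers change". Opening after Visit 2 delays no arm-specific visit.

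**The case against.** The strongest reply is that the Randomization and Allocation text is the operative one. The Study design sentence is in the future tense, whereas the later section describes a running trial: "The trial is currently recruiting patients at UCONN Dialysis/DCI and DCI Manchester". That section describes consent before it describes randomisation, and the data collection section treats enrolment as a step before baseline data. Both fit opening after consent and screening. This stands as far as it goes: the second sentence has a harmless reading. But the text does not adopt that reading, and the first sentence remains in the current protocol and resists it.

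The route to bias is also narrow. The nurse manager and nephrologist select candidates, and a licensed dentist or dental hygienist does the screening, so the coordinator does not decide periodontal eligibility. Both arms receive the same treatment through Visits 3-4, and controls receive supportive treatment at six months. This limits the risk to how and when the study is presented and how consent and screening are arranged; it does not remove it.

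Three stronger inferences are tempting and are not supported:

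- **That concealment was broken.** The protocol describes a procedure, not what was done with the envelopes.
- **That the coordinator certainly knew the arms.** The grammar leaves the opener open.
- **That the SPIRIT table proves a contradiction because allocation is listed below consent and screening.** Row order within a shared column is not chronology, and the table's alignment here is approximate.

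**Conclusion.** The point holds as a fault in the stated rule, and it should be fixed. One sentence, if followed, discloses allocations before any consent or confirmed eligibility in a unit and so defeats the concealment that the protocol claims. The other gives a different time and does not clearly repair it. This is not a detail left to a statistical analysis plan, because the protocol itself fixes the time of opening.

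No size of bias can be derived. The conclusion rests on reading the first sentence literally and on block membership being knowable before consent. If practice was already to open one envelope per consented, eligible participant, the amendment only records it.

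**What to change.** Replace both sentences with one rule, for example:

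> Within each age, race and gender block, sequentially numbered, sealed opaque envelopes are opened one at a time, only after the participant has given written consent and eligibility is confirmed. The role of the person opening the envelope and the date and time of opening are logged.

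Preferably add that opening follows completion of the Visit 2 baseline measurements. This is good practice but goes beyond what is needed to cure the contradiction. Align the SPIRIT table with the chosen order.

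The cost is a small procedural amendment, with no extra visits or patients and no delay to any arm-specific visit. The downside is that recruitment began in November 2017 and this protocol version is dated May 2018, so participants already enrolled may have been allocated under a different procedure. How their envelopes were handled should be documented and reported with the results.

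### The PI is the blinded 6-month examiner, yet sits in the annual monitoring group whose undivided data list includes un-blinded data, and nothing withholds it from the PI

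*Protocol*

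**What the plan says.** Protocol section 4, Blinding: "At 6-month visit, the final assessment will be conducted by the PI, who will be blinded to the study arm". The visit descriptions for both arms put a full mouth periodontal examination at that visit. Study Rigor and Transparency then counts blinded outcome assessment among the trial's safeguards.

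The Data and Safety Monitoring Plan says "the individuals performing the safety monitoring will be the PI, the study coordinator, an institutional colleague, who is not involved in the study", together with the IRB. On frequency: "Based on this plan, the data will be reviewed annually". One list of six data items follows, not split by recipient. Item 4 is "Analysis of outcome data and its relationship to potential changes in study design" and item 6 is "Un-blinded data". The plan adds: "The PI will evaluate the adverse events and determine whether the adverse events affect the risk/benefit ratio of the study".

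**The concern.** The person who must not know the arm at the 6-month examination is also named as a recipient of the monitoring data, and those data include an item labelled un-blinded. If item 6 means individual allocations and the list is followed as written, the PI would learn the arm of participants still to be examined.

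Probing depth, bleeding on probing, attachment level and plaque score are read by the examiner. Under Outcomes and Rationale they are secondary outcomes, and the changes in probing depth and bleeding are the stated measure of whether treatment worked clinically. They also serve Specific Aim 1. An examiner who knows that one arm had repeated care and the other a single course may read borderline sites differently. The protocol relies on the blind to exclude this at 6 months.

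**Working it through.** No sample-size or power figure bears on this point. The check compares the sections and then looks at the calendar.

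**1. The sections side by side**

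| Question | Blinding paragraph | Data and Safety Monitoring Plan |
|---|---|---|
| Role of the PI | Examiner at 6 months | Member of the monitoring group; evaluates adverse events |
| Knowledge of arm | Blinded | Item 6 of the group's list is un-blinded data |
| Who receives which item | Not addressed | One list for the whole group |
| When the PI may see arm-level data | Not addressed | Annual review, with no delay until examinations end |

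No other section divides the list, provides a closed report, or postpones the PI's access.

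**2. What item 6 could mean**

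- Individual allocations: these would directly unblind the examiner for every listed participant not yet examined.
- Summaries by arm: these do not in themselves reveal any individual's arm.
- A log of past unblinding incidents: this need not reveal an arm ahead of the examination, unless a logged participant is still to be examined and the log states the arm.

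The protocol does not say which is meant. Item 4 does not say whether the outcome analysis is pooled or by arm.

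**3. Whether reviews overlap with pending examinations**

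Inputs from Recruitment and Consent Procedures: recruitment began on 7 November 2017, and enrollment is expected to finish in April 2019. Visits are timed from Day 0, which cannot precede enrollment.

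- Last 6-month examinations: April 2019 + 6 months = October 2019, or later if Day 0 lags enrollment.
- First enrollment to last examination: November 2017 to October 2019 = 23 months.
- Reviews are 12 months apart. Since 23 > 12, at least one falls inside this period whatever month is chosen.
- If the yearly cycle is counted from the start of recruitment (an assumption), the first review is in November 2018, 11 months before October 2019.

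So, on the recruitment dates, the PI would attend at least one review with blinded examinations still to perform. The General Time Table gives an earlier expected completion, November 2018. That cannot be met if enrollment runs to April 2019, so the recruitment dates are used here.

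**4. Which outcomes are exposed**

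CRP is the primary outcome and is measured by ELISA on coded samples (Blood Collection and Analyses), so the examiner's knowledge does not reach it. No blind is stated for the 2- and 4-month examinations. That leaves the examiner-read measures at 6 months.

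**The case against.** The strongest reply is that the protocol says outright that the PI will be blinded and nowhere says that the PI receives allocations. The conflict rests on one undefined list item. Coming directly after protocol deviations, it could well mean records of unblinding incidents. The protocol also refers to a monitoring plan submitted to the IRB, which may settle who sees what. All of this is fair, and it is why the blind cannot be called broken. It does not remove the conflict: the protocol's own account of monitoring names the PI as a recipient, lists the item, and makes no exception.

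Three stronger readings are tempting but not supported.

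- A reader might infer that routine files already unblind the PI. The 6-month visit is Visit 10 in the Test arm and Visit 7 in the Control arm, charts note the procedures done, and "Access to study data will be restricted to the PI and Co-Is as well as the study key personnel". But that sentence limits access for confidentiality. No section says that the PI consults those files before examining, and the envelopes and the master visit log are handled by the study coordinator.
- A reader might estimate the share of participants enrolled but not yet examined at a given review. This needs a review date, an accrual pattern and the display of individual allocations, none of which the protocol gives. The page stamp "IRB APPROVAL DATE: 06/07/2018" dates an IRB approval, not a monitoring review.
- A reader might extend the risk to the trial's main conclusion. The primary outcome is a laboratory assay and is not exposed.

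**Conclusion.** The point holds as a conflict in the text that should be corrected. The protocol makes the PI its only blinded examiner and also a member of a group whose undivided list includes un-blinded data, with nothing to withhold those data until the 6-month examinations are complete. At least one annual review would fall while examinations are pending, given the stated recruitment dates and reviews held yearly as planned.

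The consequence is limited to four examiner-read secondary outcomes at one of three follow-up examinations in a feasibility trial. Whether any participant's arm would be shown depends on the meaning of item 6. The number affected and the size of any bias cannot be derived from the document.

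**What to change.** Reconcile the Blinding paragraph with the Data and Safety Monitoring Plan:

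- Define what item 6 contains.
- State that un-blinded or by-arm data go only to the uninvolved institutional colleague and the IRB until the last 6-month examination is done.
- Give the PI pooled data until then.
- If the PI must learn a participant's arm to evaluate an adverse event, record that participant's 6-month examination as unblinded.

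The cost is a few sentences and a pooled version of the report. No new staff are needed, because the colleague and the IRB are already named. The downside is that, until the last 6-month examination, the PI learns by-arm safety only through that colleague or the IRB. The wording should therefore say how they alert the PI if the balance of risk and benefit appears to change. Masking every chart and visit number is not needed to resolve this conflict.
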